11.3. Study Population Data

Patient disposition, demographics and baseline characteristics, prior and concomitant medications will be tabulated.

11.4. Efficacy Analyses

Not applicable.

11.5. Pharmacokinetic/Pharmacodynamic Analyses

11.5.1. Pharmacokinetic Analyses

Plasma concentration-time data for edoxaban and metabolites (if data are available) will be listed by patient, age cohort and/or dose group, and measurement time interval, and will be plotted and summarized using descriptive statistics, as appropriate.

Plasma concentration-time data for edoxaban and metabolites will be analyzed using model-based approaches such as nonlinear mixed effects modeling, where data from other studies may be pooled with pediatric data, and PK parameters will be calculated. The goal of this approach will be to estimate PK parameters such as CL/F and V/F in pediatric patients. Derived PK parameters such as AUC and metabolite-to-parent ratios (if data permit) for AUC will also be estimated. Estimated PK parameters will be assessed for age dependencies using graphical and/or modeling methods. Estimated PK parameters will be listed and summarized by age cohort and/or dose group using descriptive statistics.

An exploratory analysis of variance model will be applied to natural log-transformed CL/F, V/F, and AUC with age cohort, dose, and age cohort by dose interaction as fixed factors. Appropriate adjustments on parameters, e.g., dose-normalization on AUC, or body weight-normalization on CL/F and V/F, might also be explored. The least-squares mean differences between age cohorts with age cohort of 12 to < 18 years as the reference and the corresponding 95% confidence intervals (CIs) will be exponentiated to obtain point estimates of ratios of geometric means and the corresponding 95% CIs by dose level and/or overall (as appropriate).

11.5.2. Pharmacodynamic Analyses

For PD biomarkers (PT, aPTT, and anti-FXa), observed, change-from-baseline, and percent-change-from-baseline data will be listed by patient, age cohort and/or dose group, and measurement time interval, and will be plotted and summarized using descriptive statistics, as appropriate.

The PK/PD relationships will be examined graphically to assess age dependencies. Additional PK/PD modeling may be conducted, if necessary, to understand age dependencies.

11.6. Safety Analyses

All analyses involving safety data (physical examination, vital signs, AEs, clinical laboratory tests [hematology, serum chemistry, and urinalysis]) will be based on the safety analysis set.

11.6.1. Adverse Event Analyses

Adverse events will be coded using the Medical Dictionary for Regulatory Activities (MedDRA) coding dictionary (latest version). All AEs, including SAEs, will be mapped to system organ class and preferred term and will be listed in the data listing. A TEAE is defined as an AE that emerges during treatment, having been absent pretreatment, or worsening relative to the pretreatment state. The number and percentage of patients reporting TEAEs will be tabulated for the safety analysis set by MedDRA preferred term and system organ class with a breakdown by dose, and further by relationship to study drug administered, and by severity. Listings of death events, SAEs, and AEs that lead to discontinuation of a patient will be presented.

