3.1.5. Duration of Patient Participation

Approximately 4 weeks for each patient, which will include a screening period (within 21 days of dosing), a treatment period, and a follow-up visit conducted within 10 days after dosing. However, a patient will be considered to have completed the study if they provide the last scheduled PK sample. The treatment period will consist of predose procedures occurring on Day -1 or 1, dosing on Day 1, and postdose procedures occurring postdose on Days 1, 2 (all cohorts) and Day 3 (all patients enrolled prior to Version 5.0 of the protocol may have had Day 3 PK samples obtained). The treatment period days may occur as in-patient or out-patient based on the clinic's ability/discretion. The overnight stays are not mandatory. Check-out procedures will be performed after the last PK/PD blood samples are collected.

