4.1.1. Inclusion Criteria

Male and female pediatric patients who may require or are currently on anticoagulant therapy may be enrolled.

These may include:

- Patients who have a recently acquired or Investigator determined ongoing risk of thromboembolic events (e.g., patients with thrombophilia, congenital heart disease, presence of a central venous catheter and prior VTE).
- Patients who are completing their standard-of-care anticoagulant therapy. Edoxaban can be initiated 12 hours after cessation of enoxaparin, dabigatran, or apixaban therapy (A-U136, A-U151, and A-E152) and 24 hours after cessation of rivaroxaban therapy (A-U151). Note: that the dose of edoxaban should be at the time of the next scheduled standard-of-care anticoagulant administration:
 - At least 4 hours after last dose of unfractionated heparin.
 - At least 12 hours after last dose of bid LMWH.
 - At least 24 hours after last dose of qd LMWH and SP Xa inhibitors.
 - For patients who were on a prior vitamin K antagonist (e.g., warfarin [C-U122] and any other anticoagulants) therapy, INR value should be ≤ 2.5 prior to edoxaban dosing. If the patient's INR is > 2.5 , the patient's INR should be monitored until it is ≤ 2.5 .

- Patients who are currently treated for VTE with at least 5 days of heparin may interrupt their standard-of-care anticoagulant therapy for edoxaban administration. The dose of edoxaban should be:
 - At least 12 hours from last dose of bid LMWH, with a restart of LMWH 24 hours after edoxaban dose.
 - At least 24 hours from last dose of qd LMWH, with a restart of LMWH 24 hours after edoxaban dose.
- Patients with cardiac conditions who may require anticoagulant therapy.
- Patients with sickle cell disease who may require anticoagulant therapy.

For any condition, anticoagulant treatment interruption or discontinuation should not take place if the patient is at increased risk and should be appropriate as per standard-of-care practices.

Patients must satisfy all of the following criteria to be included in the study. Any temporal changes in the following criteria that may prohibit patient consideration, but should normalize for future eligibility, should be reassessed for the patient's future participation in the study:

1. Patients/legal guardian(s) must be able to provide written informed assent (patient, when applicable) and ICFs (signed by parent/legal guardian) prior to participating in the study.

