9. SAFETY ASSESSMENTS

9.1. Adverse Events

All clinical AEs occurring after the patient (or parent/guardian) signs the ICF and through the follow-up visit (up to 10 days after the last dose), whether observed by the Investigator or reported by the patient or patient's parent/guardian, will be recorded on the AE CRF page. Medical conditions (including laboratory values/vital signs that are out of range) that were diagnosed or known to exist prior to informed consent will be recorded as part of medical history. All SAEs are to be reported according to the procedures in Section 9.4 SAE Reporting-Procedure for Investigators. Investigator diagnosis will be recorded. Always report a diagnosis as the AE or SAE term. When a diagnosis is unavailable, report the primary sign or symptom as the AE or SAE term with additional details included in the narrative until the diagnosis becomes available. If the signs and symptoms are distinct and do not suggest a common diagnosis, report them as individual entries of AE or SAE. For events that are serious due to hospitalization, the reason for hospitalization must be reported as the SAE (diagnosis or symptom requiring hospitalization). A procedure is not an AE or SAE, but the reason for the procedure may be an AE or SAE. Pre-planned (prior to signing the ICF) procedures or treatments requiring hospitalization for pre-existing conditions which do not worsen in severity should not be reported as SAEs (see Section 9.3.2 for definitions). For deaths, the underlying or immediate cause of death should always be reported as an SAE. In addition, any serious, untoward event that may occur subsequent to the reporting period that the Investigator assesses as related to study drug should also be reported and managed as an SAE.

Each day the Investigator will determine whether any AEs have occurred by evaluating the patient. Adverse events may be directly observed, reported spontaneously by the patient (or parent/guardian) or by questioning the patient at each study visit. Patients should be questioned in a general way, without asking about the occurrence of any specific symptoms. All laboratory values must be appraised by the Investigator as to clinical significance. All abnormal laboratory values considered clinically significant by the Investigator must be recorded as an AE on the CRF, and if serious, reported as an SAE following the procedures in Section 9.4.

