9.3.4. Causality Assessment

The Investigator should assess causal relationship between an AE and the IP on the basis of his/her clinical judgment and the following definitions. The causality assessment should be made based on the available information and can be updated as new information becomes available.

- 1 = Related:
 - The AE follows a reasonable temporal sequence from study drug administration and cannot be reasonably explained by the patient's clinical state or other factors (e.g., disease under study, concurrent diseases, and concomitant medications).
 - The AE follows a reasonable temporal sequence from study drug administration and is a known reaction to the drug under study or its chemical group or is predicted by known pharmacology.
- 2 = Not Related:
 - The AE does not follow a reasonable sequence from study product administration or can be reasonably explained by the patient's clinical state or other factors (e.g., disease under study, concurrent diseases, and concomitant medications).

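### The TEAE definition sets no window after a single dose, and nothing separates adverse events or 24-36 h PD samples that follow the protocol-specified LMWH restart

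*Combined protocol and SAP*

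**What the plan says.** Section 11.6.1 defines treatment emergence as follows: "A TEAE is defined as an AE that emerges during treatment, having been absent pretreatment, or worsening relative to the pretreatment state". It names no start time, end time or number of days. TEAEs are then tabulated "with a breakdown by dose, and further by relationship to study drug administered, and by severity".

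Three other sections bear on how that definition works after a single dose:

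- Section 9.1 sets how long adverse events are collected: from consent "through the follow-up visit (up to 10 days after the last dose").
- Section 3.1.5 describes a treatment period made up of predose procedures, dosing, and "postdose procedures occurring postdose on Days 1, 2 (all cohorts) and Day 3", the last for patients enrolled before Version 5.0. The follow-up visit is listed separately.
- Section 4.1.1 says: "Patients who are currently treated for VTE with at least 5 days of heparin may interrupt their standard-of-care anticoagulant therapy for edoxaban administration". For these patients the edoxaban dose comes "with a restart of LMWH 24 hours after edoxaban dose". The synopsis and Section 1.5 say the same.

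On pharmacodynamics, Section 8.2.1 places the last PT, aPTT and anti-FXa sample of Cohorts 1, 2 and 3 at 24 to 36 hours. Cohorts 4 and 5 have one postdose PD sample, at 0.5 to 2 hours. Section 11.5.2 summarizes observed values and changes from baseline by time interval and does not mention other anticoagulants. Section 11.1.2 excludes patients with clinically significant events or protocol deviations that compromise the PD results.

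**The concern.** The plan schedules a second anticoagulant inside the observation period of some patients, but the analysis takes no account of it. A bleed that starts after LMWH is resumed goes into the same table cell as a bleed on edoxaban alone. A coagulation test taken after the restart is summarized as an effect of edoxaban.

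Safety and PD effects are both secondary objectives (Section 2.1.2), and the study is meant to guide Phase 3 dose selection (Section 1.2). Dose groups have 6 patients, so a few affected values could create or hide a dose or age pattern. Because the restart follows the protocol, the usual exclusion for deviations does not catch it.

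**Working it through.** The plan states no figure on this point. The check sets the windows side by side and works out what falls after the restart.

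**1. Share of the TEAE window after a 24 h restart.** The definition can be read in two ways: it ends with the treatment period, or it covers all collected time after the dose. For a patient who restarts at 24 h, the share is (end − 24) / end:

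| Reading | End of window | Share after restart |
|---|---|---|
| Treatment period, end of the Day 2 sampling window | 36 h | 12/36 = 33% |
| Treatment period, end of the Day 3 sampling window (enrolled before Version 5.0) | 54 h | 30/54 = 56% |
| Collection to day 10 | 240 h | 216/240 = 90% |

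No reading brings the share to zero. These are shares of time for a patient who restarts, not shares of events.

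**2. Edoxaban remaining.** Section 1.1.1.5 gives an adult oral half-life of 10 to 14 h. Assuming simple terminal decay, the fraction left at time t is 2^(−t / half-life):

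- 24 h: 2^(−24/10) = 19% to 2^(−24/14) = 30%
- 48 h: 2^(−48/10) = 4% to 2^(−48/14) = 9%
- 240 h is 240/14 = 17 to 240/10 = 24 half-lives

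The same section gives steady-state peak and trough levels of 303 and 15.5 ng/mL for 60 mg in adults. That puts the trough at 15.5/303 = 5% of the peak, below the simple-decay figure. Bleeding soon after the restart may involve both drugs. Most of a 10-day window is largely free of edoxaban. These are adult figures, and Section 1.1.1.4 expects maturation to alter the PK.

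**3. The relationship breakdown.** Under Section 9.3.4, an event is Related if it follows in reasonable sequence and "is a known reaction to the drug under study or its chemical group or is predicted by known pharmacology". That criterion does not ask for other causes to be ruled out, and bleeding is predicted by the pharmacology of a factor Xa inhibitor. An event is Not Related if it "does not follow a reasonable sequence from study product administration or can be reasonably explained by" other factors, with concomitant medication given as an example. A bleed shortly after the LMWH restart can meet both definitions. The overall TEAE table by dose stays mixed whichever box is ticked.

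**4. The 24-36 h PD sample.** The sampling window opens at the hour of the scheduled restart, so a sample can be taken up to 36 − 24 = 12 h after it. The documents accept that anticoagulants alter these tests: exclusion criterion 1 exempts coagulation abnormalities that anticoagulant therapy explains, and Section 17.2.2 warns about heparin contamination of samples. A restart that the protocol prescribes is not a deviation, so Section 11.1.2 does not remove the value, and Section 11.5.2 has no flag for it. In the PK/PD plots these points pair a low edoxaban concentration with a response that may come from LMWH.

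**5. Sensitivity of the tables.** One patient is 1/6 = 17 percentage points of a dose group within a cohort, or 1/30 = 3 points if a dose level is pooled over five cohorts of 6. If k of 6 PD values carry an LMWH effect of size d, the group mean at 24-36 h moves by (k/6) × d. The documents give neither k nor d.

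**The case against.** The strongest case on the other side has five parts.

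- **The definition does not say 10 days.** A reader might infer that every event up to day 10 counts as treatment-emergent. The documents do not support that. The 10 days belong to the collection rule in Section 9.1, an event must be new or worsened to qualify, and Section 3.1.5 allows a reading in which treatment ends on Day 2 or Day 3. This stands: the defect is an undefined window, not a stated 10-day one.
- **Safeguards exist.** TEAEs are broken down by relationship and severity, all adverse events are listed, and Section 5.2 requires all medication to be recorded. This stands in part. Recording makes a split possible, but no planned analysis uses it, and the relationship categories overlap where it matters.
- **Scope is narrow.** The 24 h restart applies to one of five listed eligibility categories, whose share is not stated. This stands.
- **The study is descriptive.** With 6 patients per dose group, a split leaves very small cells, and a reader of the listings could sort out individual cases. The small cells are a real cost. The listings do not correct the PD means, which are the planned summaries.
- **Details may lie elsewhere.** Section 11.2 defers complete details to a separate SAP whose text was not available here, and the CRF fields are not shown. Either could settle the window or already capture the time. This stands as a condition on the conclusion.

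**Conclusion.** The point holds in a limited form. The TEAE window is undefined for a single dose. On either reading, time on protocol-specified LMWH can fall inside it, so some bleeding on LMWH can be tabulated under the edoxaban dose. In Cohorts 1 to 3 the last PD summary point can reflect LMWH, and nothing in Sections 11.1.2 or 11.5.2 prevents that.

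For a patient who restarts on schedule, 33% to 90% of the window follows the restart. The number of affected patients, bleeds or PD values cannot be computed, because the size of the category is not given.

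A reader might go further and infer that most tabulated events would arise on LMWH. That would require every patient to restart, a 10-day TEAE window, and an event rate that the documents do not supply. Nor does the point reach the PD data of Cohorts 4 and 5, whose only postdose sample is at 0.5 to 2 h, or the modelled PK endpoints, which rest on edoxaban and metabolite concentrations measured by LC-MS/MS.

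The conclusion assumes that the separate SAP does not already define the window or flag post-restart data. It is a low-cost improvement to the analysis, but more than a missing detail: as written, 11.5.2 would average LMWH-affected values into the edoxaban PD summary.

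**What to change.** - **Data.** Record the date and clock time of the first postdose dose of any other anticoagulant. Record onset time for adverse events starting on that date, with a stated rule for events that cannot be ordered.
- **Section 11.5.2.** Flag PD samples drawn after that dose. Keep them in the listings, leave them out of the edoxaban PD summaries and PK/PD plots, and report how many were left out of each group.
- **Section 11.6.1.** State the start and end of the TEAE window. Beside the overall TEAE table, show TEAEs, with bleeding separate, by onset before or after the first dose of another anticoagulant. Show patients who did not resume one separately.
- **No fixed time cut.** Five adult half-lives (5 × 10 = 50 h to 5 × 14 = 70 h), or 72 h as a rounded limit, may look natural. It would carry an adult half-life into infants, and the later class would pool patients who resumed an anticoagulant with those who did not.

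The cost is a time field if the CRF lacks one, a few sentences in the analysis text, and one added table layout. The downside is small counts per cell and fewer 24-36 h PD values in Cohorts 1 to 3. The overall TEAE table is kept, so no safety information is lost. No change to the clinical restart rule is proposed.

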11.6.2. Clinical Laboratory Evaluation Analyses

Standard hematology, serum chemistry, coagulation, and urinalysis at each planned assessment and change from baseline at each planned post-baseline assessment will be summarized for the safety analysis set by dose. Patients with abnormal values will be noted in the data listings.

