This is a Phase 1, open-label, multiple-center study in pediatric patients from 38 weeks gestation to < 18 years of age. Patients from 5 age cohorts (12 evaluable patients per age cohort) will receive a single dose of edoxaban. Each age cohort will be divided into a low- and high-dose group (6 patients per dose group). Order of enrollment will be from the oldest age cohort to the youngest age cohort. Within each age cohort, enrollment will first start in the lower dose group (to achieve exposures comparable to a 30 mg adult dose). After evaluation of PK and safety data from at least half the patients in the lower dose group, enrollment may then start in the higher dose group (to achieve exposures comparable to a 60 mg adult dose). If the observed exposures are higher than expected in the lower dose group and exceed the projected 60 mg adult exposure, then a lower dose may be investigated in the proposed “high-dose” group. Enrollment in the next younger age cohorts will begin when at least 50% of patients have completed the study in the older age cohort. Enrollment in the younger age cohorts will start only after PK and safety data have been evaluated from at least 6 patients (3 low-dose and 3 high-dose) in the older age cohort. Pharmacokinetic and safety data will be reviewed by a Data and Safety Monitoring Board (see Section 11.9) who will approve the start of the next younger age cohort. However, enrollment initiation of Cohort 5 may be considered without PK and safety data from at least 50% of patients in the preceding older dose group.

Age cohorts and dose groups:

- 12 to < 18 years of age on the day of dosing (12 evaluable total patients)
 - Cohort 1a: Low-dose group (6 patients)
 - Cohort 1b: High-dose group (6 patients)
 - 6 to < 12 years of age on the day of dosing (12 evaluable total patients)
 - Cohort 2a: Low-dose group (6 patients)
 - Cohort 2b: High-dose group (6 patients)
-

-
- 2 to < 6 years of age on the day of dosing (12 evaluable total patients)
 - Cohort 3a: Low-dose group (6 patients)
 - Cohort 3b: High-dose group (6 patients)
 - 6 months to < 2 years of age on the day of dosing (12 evaluable total patients)
 - Cohort 4a: Low-dose group (6 patients)
 - Cohort 4b: High-dose group (6 patients)
 - 38 weeks gestation to < 6 months of age on the day of dosing (12 evaluable total patients)
 - Cohort 5a: Low-dose group (6 patients)
 - Cohort 5b: High-dose group (6 patients)

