3.1.6. Stopping Rules

Due to potential tolerability differences among age cohorts, stopping criteria will be applied independently to each age cohort. The minimum intolerable dose will be defined as (1) the dose

at which a minimum of 60% of evaluable patients in an age cohort experiences more than 1 occurrence of moderate or severe AEs, related to edoxaban or (2) the dose at which at least 1 patient in an age cohort experiences an SAE judged to be medically serious and related to edoxaban as assessed by an independent DSMB. The DSMB will be responsible for reviewing and assessing the available safety data as set forth in the DSMB Charter.

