11.2. General Statistical Considerations

Complete details of the planned statistical analyses will be included in a separate Statistical Analysis Plan. The analyses for this study will be considered descriptive and exploratory. No visit windows will be used for analysis.

In general, all data will be summarized by age cohort and dose group, and all evaluable data will be included in the analyses. For qualitative variables, the population size (N for sample size and n for available data) and the percentage/incidence (of available data) for each class of the variable will be presented. Quantitative variables will be summarized using descriptive statistics, including the population size (N for sample size and n for available data), mean, SD, coefficient of variation (CV%), median, minimum, and maximum values.

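### Adverse event and laboratory summaries are specified by dose alone, an unexplained departure from the cohort-and-dose default; on the natural reading they pool newborns with adolescents.

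*Combined protocol and SAP*

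**What the plan says.** Section 11.2 (General Statistical Considerations) sets the default layout: "In general, all data will be summarized by age cohort and dose group". It leaves the detail to another document: "Complete details of the planned statistical analyses will be included in a separate Statistical Analysis Plan".

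Two safety sections then state their own layout:

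- Section 11.6.1 tabulates TEAEs by preferred term and system organ class "with a breakdown by dose, and further by relationship to study drug administered, and by severity".
- Section 11.6.2 says that hematology, serum chemistry, coagulation and urinalysis values, and changes from baseline, "will be summarized for the safety analysis set by dose".

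Age cohort appears in neither, and no reason is given. Section 11.6.3 (vital signs) names no stratifier, so the Section 11.2 default applies there. Section 3.1.6 starts from the premise that tolerability may differ among age cohorts, and for that reason "stopping criteria will be applied independently to each age cohort".

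**The concern.** Evaluating safety and tolerability is a secondary objective (Section 2.1.2), and enrollment is staggered from oldest to youngest. A reader will want to know whether the youngest children tolerated the drug as well as the adolescents did. A table split only by dose level cannot answer that, because an excess confined to one cohort is averaged over the other four.

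For laboratory values the pooled mean is also hard to interpret. The protocol itself reports that baseline coagulation activity differs between cord and adult blood (Sections 1.1.1.4 and 1.3) and that renal function matures during the first year of life (Section 1.1.1.4). Pooling by level would also mix formulations, since Cohort 1 takes tablets and Cohorts 2 to 5 take the suspension (Section 3.1.2).

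**Working it through.** The plan gives no figure on this point to reproduce. The check has three parts: what dose means, which tables are affected, and how large the effect could be.

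**1. What dose means in Section 11.6.** Three readings are possible.

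- *Low or high level.* Section 11.5.1 lists age cohort, dose and their interaction as separate fixed factors and reports results by dose level, so dose is there crossed with cohort. Where the authors want cohort in the layout they name it (Sections 11.5.1, 11.5.2 and 11.7.1). This is the natural reading.
- *The nested groups 1a to 5b* (Section 3.1.1). On this reading nothing is pooled across ages.
- *The amount in mg.* Individual doses depend on age cohort, body weight and targeted exposure (Section 3.2.1.2), so the columns would be neither fixed nor two in number.

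**2. Which tables are affected on the low/high reading.** The design has 5 cohorts with 6 patients per dose group (Section 3.1.1).

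- Patients per pooled column: 5 × 6 = 30. Patients per cohort-by-dose cell: 6.
- TEAEs, and hematology and coagulation at screening and follow-up, are collected in all cohorts (Sections 6.4, 9.1 and 9.6), so all five cohorts are pooled.
- Serum chemistry is measured in all cohorts at screening but only in Cohorts 1 to 3 at follow-up (Section 9.6; Table 17.1, note 5). A by-level table would hold 30 patients per column at baseline and 3 × 6 = 18 for follow-up and change. Post-baseline chemistry therefore does not pool infants with adolescents, but the shell would not show that the two youngest cohorts contribute nothing.
- Urinalysis is scheduled only at screening and check-in (Section 9.6, Table 17.1), so there is no scheduled postdose value to pool.

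**3. Size of the effect.** Take, as an assumption, an event in 3 of the 6 patients in one infant dose group. The exact (Clopper-Pearson) 95% limits for x of n are the 2.5% quantile of Beta(x, n − x + 1) and the 97.5% quantile of Beta(x + 1, n − x).

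| Layout | x/n | Proportion | 95% CI |
|---|---|---|---|
| Cohort by dose group | 3/6 | 50% | 11.8% to 88.2% |
| Dose level, no events in other cohorts | 3/30 | 10% | 2.1% to 26.5% |

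The dilution is 50% / 10% = 5-fold. It depends on the number y of patients with the event among the other 24 at that level, because the pooled proportion is (3 + y)/30:

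- y = 0: 3/30 = 10%, 5-fold.
- y = 2: 5/30 = 16.7%, 3-fold.
- y = 12: 15/30 = 50%, no dilution, since 12/24 is also 50%.

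Five-fold is therefore the largest dilution. It applies to a signal found only in one cohort.

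**The case against.** Several points on the other side stand.

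- *The default allows exceptions.* Section 11.2 is qualified as a general rule, so a section-specific layout does not strictly contradict it. What remains is a departure without a stated reason.
- *A reader might infer that the tables contradict the stopping rule.* The documents do not support this. Section 3.1.6 is a decision rule applied during the study, and "The DSMB will be responsible for reviewing and assessing the available safety data as set forth in the DSMB Charter". Nothing makes the Section 11.6 tables the input to that review. Nor would tables by cohort show by themselves whether the first criterion was met: it refers to the dose "at which a minimum of 60% of evaluable patients in an age cohort experiences more than 1 occurrence of moderate or severe AEs", which is not the quantity an ordinary TEAE incidence table displays.
- *A reader might infer that a signal in infants would be lost.* It would not. All adverse events are listed, with listings of deaths, serious events and discontinuations (Section 11.6.1), and abnormal laboratory values are noted in listings (Section 11.6.2). In a study of 60 patients such a pattern could be found there. The loss is in the summary rates that readers usually rely on.
- *Dose is undefined.* On the nested reading nothing is pooled. That reading fits less well with Section 11.5.1, but the text does not exclude it.
- *The separate Statistical Analysis Plan may already fix the layout.* Its text is not in the documents under review, so this could not be checked.

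**Conclusion.** The point holds as an inconsistency of specification. Sections 11.6.1 and 11.6.2 name dose alone, where the default names age cohort and dose group. On the natural low/high reading, TEAE, hematology, coagulation and pre-dose laboratory tables would pool all five cohorts, and a signal confined to one of them could be shown at as little as one fifth of its rate.

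This rests on four assumptions: dose means low or high level; cells have the planned 6 patients (the safety set includes everyone dosed, so actual counts may differ slightly); no other cohort has the event; and the separate analysis plan does not override the wording. The finding does not extend to post-baseline serum chemistry, postdose urinalysis or vital signs. Sample size, power, data collection and the safety board's review are unaffected. The change is worth making because it costs little and serves a stated objective.

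**What to change.** - In Sections 11.6.1 and 11.6.2, replace the by-dose layout with one by age cohort and dose group (low/high). This also settles what dose means.
- Give totals across cohorts for TEAE counts only. A total for laboratory means would bring back the pooled average that is hard to interpret.
- In Section 11.6.2, state that serum chemistry change from baseline applies to Cohorts 1 to 3 only.
- Leave Section 11.6.3 as it is, because Section 11.2 already governs it.
- Check that the separate Statistical Analysis Plan and its table shells agree.

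The cost is wording and table shells: ten cohort-by-dose cells (5 × 2) in place of two columns. The downside is wider tables with 6 patients per cell, where percentages move in steps of 1/6 (16.7 points). Counts should therefore be shown beside percentages.
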